2.2 Analysis sets

The **Randomized Set** (RAS) consists of all randomized patients.

The **Full Analysis Set** (FAS) comprises all subjects who receive at least one IVT injection of the study treatment. The FAS will serve as the primary analysis set for all efficacy analyses. According to the intent to treat principle, subjects will be analyzed according to the treatment they have been assigned to during the randomization procedure.

The **Safety Set** includes all subjects who received at least one dose of study treatment. Subjects will be analyzed according to the study treatment received, where treatment received is defined as the actual treatment regime. If the subject took only one dose of study treatment, the subject will be analysed according to the randomized treatment regime.

Relevant protocol deviations and their potential impact on the analysis will be assessed and adequately documented / processed before database lock.

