6.5 Dose escalation and dose modification

No study treatment dose modification is allowed.

Deviations from dose intervals during the initiation phase and/or dose adjustments during the whole study are not allowed.

Interruption of study treatment is allowed if warranted by an AE.

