12.1 Analysis sets

The **Randomized Analysis Set (RAS)** consists of all randomized subjects.

The **Full Analysis Set (FAS)** comprises all subjects who receive at least one IVT injection of the study treatment. The FAS will serve as the primary analysis set for all efficacy analyses. According to the intent to treat principle, subjects will be analyzed according to the treatment they have been assigned to during the randomization procedure.

The **Safety Set** includes all subjects who received at least one dose of study treatment. Subjects will be analyzed according to the study treatment received, where treatment received is defined as the randomized treatment if the subject took at least one dose of that treatment or the first treatment received if the randomized treatment was never received.

Relevant protocol deviations and their potential impact on the analysis will be assessed and adequately documented / processed before database lock.

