1.1 Study design

This study is a 52-week, randomized, open-label, multi-center, two-arm study for pretreated patients with suboptimal anatomically controlled nAMD.

Consenting patients will participate in a screening period, lasting up to 14 days. Eligible patients will be randomized in a 1:1 ratio to one of the two treatment arms:

- Brolucizumab 6 mg “loading arm”: 3 x 4-weekly initial injections followed by an injection every 12 weeks
- Brolucizumab 6 mg “non-loading arm”: one initial injection followed by an injection every 12 weeks

There are three periods in this study (see Figure 1.1):

- Screening period: from day -14 to Baseline
- Open-label treatment period: from Baseline (day 1) to week 48
- Post-treatment follow-up period: from week 48 to week 52

[figure not shown]

Figure 1.1 Study Design

1. Screening period: Day-14 to day -1

A screening period of up to 2 weeks will be used to assess eligibility.

One time rescreening of patients is allowed, except for the purpose of capturing new BCVA or imaging assessments that previously failed to qualify the patient. As long as testing can be repeated within 14 days of the first screening, the other screening assessments do not need to be repeated. If rescreening is to occur beyond 14 days from the original screening visit date, then all screening procedures must be repeated. Medical judgment should be exercised to ensure that treatment of nAMD is not withheld in order for a patient to participate in the study.

2. Open-label treatment period: Day 1 to Week 48

After confirmation of eligibility, patients will be randomized in a 1:1 ratio to one of the treatment arms.

Only one eye will be selected as study eye and treated with study medication.

The baseline visit is defined as Day 1/Visit 1, and end of treatment visit as Visit 13 (Week 48).

A study visit schedule will be established at the time of randomization for all patients with study visits scheduled every 4 weeks. All efforts should be made to adhere to this study visit schedule ± 7 day window. Treatment is intended to be administered on the day of study visit, or if this is not possible, within 3 days after the study visit when the per-protocol assessments took place. In addition, for a given protocol visit, assessments can be performed on two consecutive days.

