In the “loading arm”, patients will receive three consecutive injections every 4 weeks at baseline, weeks 4 and 8, which should be at least 21 days apart, followed by an injection every 12 weeks. In the “non-loading arm”, patients will receive one initial injection followed by an injection every 12 weeks. For both study arms the assessment of disease activity will be performed 8 and 12 weeks after the previous injection. If disease activity is identified by the investigator for the first time at any visit after / from week 8 respectively, patients should stay on a q12w dosing, if the decline in BCVA is clinically non-significant (BCVA loss < 4 ETDRS letters) compared to the previous visit. If after / from week 8 BCVA-loss of ≥ 5 ETDRS letters appears compared to the previous visit or disease activity is identified for a second time based on the investigator’s judgment of visual and / or anatomic outcomes and signs of disease activity, patients must be assigned to q8w dosing. One attempt of interval re-extension from q8w to q12w treatment will be allowed based on the investigator’s judgement if no disease activity (DA) is detected during the subsequent visit(s). If the patient shows significant DA at any visit after the re-extension attempt, injection intervals will be fixed to q8w until the end of the study.

Patients who require injections more frequently than every 8 weeks after the loading phase (week 8, loading arm) or baseline (non-loading arm) will be discontinued from further study treatment.

3. Post-treatment follow-up period: Week 48 to week 52

For all patients, the last study assessment will be performed at week 52.

Patients withdrawn from the study prior to study completion will be asked to return for an early discontinuation visit (EOS / Visit 14), four weeks (± 7 days) following their last study visit.

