2.1.1 General definitions

The term study treatment is used for Brolucizumab 6 mg/0.05 mL.

The baseline visit is defined as day 1/visit 1.

The on-treatment period lasts from the date of first administration of study treatment to 30 days after the last administration of study treatment (EOT) or EOS whichever is the latest.

Calculation of treatment interval:

- “Mean treatment interval from week 8 to week 52”: (last injection – first injection from week 8 on*) divided by (number of injections from week 8 to week 52 -1)

*the first injection from week 8 on could be at week 8 or later.

- “Mean treatment interval in last 24 weeks prior to first brolucizumab injection” will be calculated as: (date of first brolucizumab injection - date of first anti-VEGF pre-treatment within last 24 weeks) divided by number of injections within 24 weeks prior to first brolucizumab injection.

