2.14 Interim analysis

There is no interim analysis planned.

3 Sample size calculation

Due to feasibility reasons, resulting in a substantial delay in recruitment, as described above, with Amendment 2 the recruitment will be prematurely discontinued. A final number of approximately 50 patients is expected to be recruited by the time of approval of the amendment.

As a consequence, all analyses will be performed and interpreted in a purely descriptive manner.

Based on an expected sample size of 25 patients per group, and an assumed common standard deviation of 13 letters, a precision in terms of the width of the respective 95% confidence interval for the difference in change from baseline of the visual acuity of +/- 7,21 can be achieved. Taking into account the current number of patients of (for 23 patients per group), the precision in terms of the half width of the 95% confidence interval would be 7,51.

4 Change to protocol specified analyses

The wording of secondary objective 2) was slightly changed to: "Comparison of proportions of patients maintained at a q12w interval **from baseline / upload to week 52**" instead of per protocol: "Comparison of proportions of patients maintained at a q12w interval **at week 52**".

5 Appendix

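### SAP 2.2 groups the Safety Set by an undefined actual regimen, against Protocol 12.1 and without declaring it, so safety grouping could depend on the safety outcome

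*SAP*

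**What the plan says.** Both documents say that the Safety Set is analysed by treatment received, but they define the term differently.

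- Protocol 12.1: "where treatment received is defined as the randomized treatment if the subject took at least one dose of that treatment". If the randomised treatment was never received, the first treatment received is used.
- SAP 2.2: "where treatment received is defined as the actual treatment regime". One exception follows: "If the subject took only one dose of study treatment, the subject will be analysed according to the randomized treatment regime".

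The arms differ in schedule, not in drug. SAP 2.1.1 states: "The term study treatment is used for Brolucizumab 6 mg/0.05 mL". Under SAP 1.1, loading "patients will receive three consecutive injections every 4 weeks at baseline, weeks 4 and 8" and then go to 12-weekly injections, while non-loading patients have "one initial injection followed by an injection every 12 weeks".

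Protocol 6.5 provides for missed doses: "Interruption of study treatment is allowed if warranted by an AE". SAP 2.8 runs all safety analyses on the Safety Set, by arm. SAP section 4 reports one departure from the protocol's analyses, which begins "The wording of secondary objective 2) was slightly changed to" and concerns the q12w endpoint. The Safety Set definition is not mentioned there.

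**The concern.** A grouping rule for safety should not depend on what happens to the patient after randomisation, least of all on safety events. Under the SAP rule, a patient with two or more injections counts as loading only if the injections actually given are judged to be a loading regimen. Some loading patients may miss early injections because of an adverse event or another safety finding. They could then leave the arm in which the event arose and take the event with them.

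The safety reasons that the protocol foresees remove injections and do not add them. Any movement would therefore run mainly from loading to non-loading, and would make loading look safer and non-loading less safe.

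The rule also cannot be programmed as written, because nothing says which pattern of injections counts as which regimen. Treatment is open to the clinical trial team (Protocol 6.4), so unclear cases would be decided by people who can see both arm and outcome. The exposure summaries in SAP 2.4.1 use the same set. Regrouping by injections received and then tabulating injections received would partly hide incomplete loading.

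**Working it through.** **The plan's own figure.** The plan gives no number for this point. Its one design figure supplies the arm size. The half-width of the 95% interval is 1.96 × 13 × √(2/n), which gives 7.21 letters for n = 25 and 7.51 for n = 23. Both match Protocol 12.8.1 and SAP section 3. The concern does not depend on them.

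**Step 1: what the protocol's rule does.** Every treated patient has a baseline injection of brolucizumab 6 mg, and that injection belongs to both regimens. Whether the protocol's wording is read as drug or as regimen, one injection meets the condition. Every treated patient stays in the randomised arm.

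**Step 2: what the SAP's rule does to a patient randomised to loading.**

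| Injections received | Arm under Protocol 12.1 | Arm under SAP 2.2 |
|---|---|---|
| Baseline only, then stops | Loading | Loading (one-dose exception) |
| Baseline and week 4, then stops | Loading | Not defined; resembles an incomplete loading course |
| Baseline, week 8 and later (week 4 withheld) | Loading | Not defined; to week 8, could match a non-loading patient moved to q8w |
| Baseline, then later doses (weeks 4 and 8 withheld) | Loading | Not defined; resembles non-loading |
| Baseline, weeks 4 and 8, and later | Loading | Loading |

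The third and fourth rows are where a patient could change arm. The second is where no arm is assigned.

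**Step 3: whether those rows can arise for safety reasons.** Protocol 6.5 permits interruption for an adverse event. Protocol 6.7.2 has treatment cancelled when a study-eye safety concern could be made worse by it. Protocol 8.4.3 advises against injection until raised intraocular pressure has normalised. Each can withhold an early injection without ending study treatment.

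**Step 4: size, as an illustration.** The documents give no adverse-event counts for this trial, so the counts here are assumed. With n patients per arm, e of them with an event in each arm, and k loading patients with an event moved, the rates are (e − k)/(n − k) for loading and (e + k)/(n + k) for non-loading.

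| n | e | k | Loading | Non-loading | Gap (points) |
|---|---|---|---|---|---|
| 25 | 5 | 0 | 5/25 = 20.0% | 5/25 = 20.0% | 0.0 |
| 25 | 5 | 1 | 4/24 = 16.7% | 6/26 = 23.1% | 6.4 |
| 25 | 5 | 2 | 3/23 = 13.0% | 7/27 = 25.9% | 12.9 |
| 25 | 3 | 1 | 2/24 = 8.3% | 4/26 = 15.4% | 7.1 |
| 23 | 5 | 1 | 4/22 = 18.2% | 6/24 = 25.0% | 6.8 |
| 23 | 3 | 1 | 2/22 = 9.1% | 4/24 = 16.7% | 7.6 |

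With no true difference, one moved patient creates a gap of about 6 to 8 points.

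**The case against.** The strongest objection concerns intraocular inflammation (IOI), the event of most interest with this drug. A reader might infer that IOI during loading would be shifted to the non-loading arm, and might size that shift from the IOI rates in Protocol 4.5. The documents do not support this. Protocol 9.1.1 requires study treatment to stop, not pause, when IOI, retinal vasculitis or retinal vascular occlusion develops. After the first injection, the one-dose exception then keeps the patient in loading. After baseline and week 4, the pattern resembles only an incomplete loading course. After week 8, loading is complete. IOI itself therefore does not turn a loading patient into a non-loading one, although after two injections the SAP leaves the arm undefined.

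Other objections have weight:

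- The exposed group is narrow. It needs an interruptible event, a withheld early injection and a later resumption. Protocol 6.5 also forbids deviations from the initiation intervals.
- Safety is descriptive, with no formal hypotheses and about 50 patients. The safety objective is not worded as a comparison of arms.
- Injection data are listed, injections to week 8 are shown by visit, and adverse events are displayed by subject, so a careful reader could trace a regrouped patient.
- Protocol section 12 leaves further detail to the SAP.

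These points limit the consequence but do not remove the conflict. The tables are still presented by arm, and in a small descriptive trial readers will take the percentages at face value. Adding detail is also different from replacing a definition that the protocol already gives.

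**Conclusion.** The concern holds in a conditional form. Three things can be read directly from the documents: SAP 2.2 conflicts with Protocol 12.1, SAP section 4 does not declare the change, and the actual regimen has no classification rule. From these it follows that safety grouping could depend on the safety outcome for loading patients who miss an early injection for an interruptible reason and later resume. It also follows that a patient who stops after baseline and week 4 has no assigned arm.

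It would go too far to say that the safety comparison is biased. The number of such patients is unknown and may be zero. The gap of about 6 to 8 points per moved patient rests on assumed counts of 3 or 5 patients with an event per arm, arms of 23 or 25, and equal true rates. The efficacy analyses use the Full Analysis Set by randomised arm and are not affected.

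**What to change.** - Restore the Protocol 12.1 definition in SAP 2.2, so that every treated patient is analysed for safety in the randomised arm.
- Add a listing of patients whose loading injections departed from plan, with the reason.
- If the sponsor wants an as-received view, make it supplementary, state which injection patterns count as which regimen (including partial loading courses), and declare it in SAP section 4.

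The cost is SAP wording and one listing drawn from injection data already collected. If the safety tables have already been programmed, the treatment grouping variable has to be re-derived and the tables rerun. No new data are needed, and trial conduct does not change.

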2.2.1 Subgroup of interest

No subgroup analyses are planned.

2.3 Patient disposition, demographics and other baseline characteristics

2.3.1 Patient disposition

Using all enrolled patients the number of patients screened, randomized, discontinued prematurely and completed treatment/ study by center and treatment will be displayed. For patients who discontinued/ completed treatment/ study percentages are computed using the number of randomized patients.

Furthermore, a listing will be provided for first patient first visit and last patient last visit by center.

In addition, the frequency of patients who completed/ discontinued is displayed separately for screening phase (all enrolled patients), for treatment completion (Randomized Set) and for study completion (Randomized Set) and the reason for discontinuation is analysed according to CRF-given categories.

2.3.2 Demographics and other baseline characteristics

Demographics and other baseline data including disease characteristics will be listed and summarized descriptively by treatment arm for the FAS and Safety set.

Categorical data will be presented as frequencies and percentages. For continuous data, mean, standard deviation, median, minimum, and maximum will be presented. For selected parameters, 25th and 75th percentiles will also be presented.

Relevant medical history (including underlying inflammation, autoimmune disease), nAMD history and current medical conditions at baseline will be summarized separately by system organ class (SOC) and preferred term of the MedDRA dictionary, by treatment arm for the FAS.

Prior Anti-VEGF medication will be listed and last pre-treatment medication (latest injection date) will be presented as frequencies and percentages.

In addition, the number of injections within the last 24 weeks and the mean injection interval in last 24 weeks prior to first brolucizumab injection will be summarized by sample statistics.

2.4 Treatments (study treatment, rescue medication, concomitant therapies, compliance)

2.4.1 Study treatment / compliance

All collected injection data will be listed.

The duration of exposure to the investigational drug as number of injections from baseline to EOS/week 52 will be summarized by means of descriptive statistics using the safety set. Besides the total number of injections, the following treatment periods will be analysed separately:

- Baseline (day 1) to week 8: number of injections will be displayed by visit.

- Week 12 to week 48: average number of injections over this period will be displayed.

Switching from q12w to q8w dosing regime, including total number of switching patients and switching patients by visit, will be analysed by frequencies and percentages. The number of switching patients from q8w to q12w will be analysed in the same manner. The total number of switches per patient will be presented by sample statistics.

2.4.2 Prior, concomitant and post therapies

Concomitant medications and significant non-drug therapies prior to and after the start of the study treatment will be listed and summarized according to the WHO Drug Reference List, which employs the Anatomical Therapeutic Chemical (ATC) classification system, by treatment arm, using the Safety Set.

There should be no rescue medication for nAMD in the study eye.

The number of patients who reported any laser treatment will be summarized by frequency table, using the Safety Set. Details on reported laser treatment will be listed.

2.5 Analysis of the primary objective

2.5.1 Primary endpoint

The primary objective of this study is to evaluate descriptively the difference of brolucizumab 6mg with one (initial) injection followed by q12w maintenance and brolucizumab 6mg with 3x q4w loading injections followed by q12w maintenance with respect to the change in BCVA from baseline to mean of visits at week 40 to week 52. The analysis of the primary endpoint will be based on the following estimand:

Variable of interest: primary endpoint is the change in BCVA from baseline to mean of visits at week 40 to week 52; irrespective of adherence to treatment, i.e. the treatment policy.

Intervention effect: effect of brolucizumab “non-loading arm” versus “loading arm” after 52 weeks regardless of adherence to randomized treatment.

Summary measure: Difference in means.

The population will be male and female patients ≥ 50 years old diagnosed with active choroidal neovascularization (CNV) secondary to AMD and treated previously for this disease, who will be switched to brolucizumab at baseline.

2.5.2 Statistical hypothesis, model, and method of analysis

The analysis of the primary endpoint will be performed in a purely descriptive manner and non-inferiority testing will be omitted. To evaluate the outcome in terms of mean change in BCVA from baseline to mean of visits at week 40 through week 52, a two-sided 95% confidence interval for the treatment difference will be derived from a mixed model with repeated measures (MMRM) model with factors treatment arm, baseline BCVA and age. An unstructured

covariance structure shared across treatment arms was used to model the within-patient errors. Programming details are specified in section 5.4.

The FAS will be used to analyze the primary endpoint.

2.5.3 Handling of missing values/censoring/discontinuations

As a primary approach, retrieved data will be included, irrespective of intercurrent events such as prohibited medication or treatment interruption or discontinuation (treatment policy, difference in all randomized patients). For statistical analyses of continuous parameters, missing data in case of lost to follow-up will be accounted for in a mixed model for repeated measures (MMRM) assuming data after loss to follow-up are missing at random (MAR), and assuming almost all data will be retrieved. Thus, every effort must be made to follow-up on patients after treatment discontinuation up to end of study.

2.5.4 Supportive analyses

2.6 No sensitivity analyses are planned. Analysis of the key secondary objective

There is no key secondary objective. Thus this section is not applicable.

2.7 Analysis of secondary efficacy objective(s)

2.7.1 Secondary endpoints

Secondary efficacy objectives and endpoints are listed in Table 1-1.

2.7.2 Statistical hypothesis, model, and method of analysis

Secondary endpoints will be analyzed using adequate descriptive statistics, if not otherwise specified. Details on planned analyses are listed in the table below.

Table 2 Endpoints and statistical method

Endpoints for secondary objectives	Statistical method
1.Treatment interval	
1.1. Mean treatment interval (overall as well as per study group comparing treatment intervals from week 8 to week 52 in the study vs. 24 weeks to baseline prior to enrollment)	Descriptive analysis of injection intervals (weeks): Summary statistics (n,mean, SD, min, median, max) for - Mean treatment interval from week 8 to week 52 - Mean treatment interval within 24 weeks prior to baseline. - Last treatment interval under observation Box Plot for “last treatment interval under observation”. Stacked Bar Chart for patients on q8w and q12w by visit (last documented DAA).

1.2. Rate of patients (overall and per group) with prolonged interval compared to mean treatment interval in last 24 weeks to baseline prior to enrollment

- **Frequencies and percentages (n(%))** for total FAS and both treatment arms.

- **Logistic regression model**

Dependent variable: interval prolongation* (Y/N)

Factors:

- treatment arm
- baseline BCVA
- age

Odds-ratio, 95% CI and p-value.

Estimates for , non-loading arm, loading arm and difference (non-loading – loading).

* Prolongation is calculated by comparing the “mean treatment interval in last 24 weeks prior to first brolucizumab injection” (defined in section 2.3.2) with the time interval between the last two brolucizumab injections. Patients with only one injection in treatment period are calculated as non-responders (no interval prolongation).

2. Maintenance of q12w intervals

2.1. Comparison of proportions of patients maintained at a q12w interval at week 52 between the two arms

- **Frequencies and percentages (n(%))** for total FAS and both treatment arms.

- **Logistic regression model**

Dependent variable: “q12w” (Yes/No): “DAA maintained at q12w from baseline / upload to week 52”

Factors:

- treatment arm
- baseline BCVA
- age

Odds-ratio with 95% CI and p-value.

Patients who discontinued treatment prior to week 52 are calculated as non-responders.

2.2. Distributions of patients at q8w/q12w intervals from baseline to week 52

Descriptive statistics for treatment regimens:
Frequencies and percentages (n (%)) by visit

3. Functional Outcomes

3.1. Average change in BCVA from baseline to week 52

Descriptive statistics for course and change in BCVA:
Summary statistics (n,mean, SD, min, median, max) for BCVA in the study eye by visit.

3.2. Proportion of patients with BCVA improvements of ≥ 5 , ≥ 10 , and ≥ 15 letters from baseline to week 52
3.3. Proportions of BCVA ≥ 69 letters at week 52

3.4. Mean change in BCVA from baseline to mean of visits week 16 to week 28

Descriptive statistics (**rates and percentages**) for proportion of patients with:

- Gain* in BCVA of ≥ 5 ETDRS letters
- Gain* in BCVA of ≥ 10 ETDRS letters
- Gain* in BCVA of ≥ 15 ETDRS letters

*from baseline to week 52

Mixed model for repeated measures (MMRM)

Factors:

- treatment arm
- baseline BCVA
- age

Least square means with SE and 90% CI.

4. Anatomical outcomes

4.1. Change from baseline in CST as assessed by SD-OCT per visit up to week 52
4.2. Absence of IRF, SRF, and sub-RPE fluid as assessed by SD-OCT per visit up to week 52
4.3. Presence of active CNV leakage as assessed by fluorescein angiography at week 52

Descriptive analysis of anatomical outcomes:
Frequencies and percentages, **n (%)**, by visit

